7.2.4. Liver-Related Laboratory Evaluations

Liver-related abnormalities after initial study drug dosing will be examined and summarized for the B/F/TAF, Delayed Switch to B/F/TAF, and All B/F/TAF groups using the number and percentage of participants who were reported to have the following laboratory test values for post baseline measurements:

- Aspartate aminotransferase (AST): (a) $> 3 \times$ Upper limit of normal (ULN), (b) $> 5 \times$ ULN, (c) $> 10 \times$ ULN, (d) $> 20 \times$ ULN
- Alanine aminotransferase (ALT): (a) $> 3 \times$ ULN, (b) $> 5 \times$ ULN, (c) $> 10 \times$ ULN, (d) $> 20 \times$ ULN
- AST or ALT: (a) $> 3 \times$ ULN, (b) $> 5 \times$ ULN, (c) $> 10 \times$ ULN, (d) $> 20 \times$ ULN
- Total bilirubin: (a) $> 1 \times$ ULN, (b) $> 2 \times$ ULN
- Alkaline phosphatase (ALP) $> 1.5 \times$ ULN
- AST or ALT $> 3 \times$ ULN and total bilirubin: (a) $> 1.5 \times$ ULN, (b) $> 2 \times$ ULN
- AST or ALT $> 3 \times$ ULN and total bilirubin $> 2 \times$ ULN and ALP $< 2 \times$ ULN

For individual laboratory tests, participants will be counted once based on the most severe postbaseline value. For both the composite endpoint of AST or ALT and total bilirubin, and the composite endpoint of AST or ALT, total bilirubin, and ALP, participants will be counted once when the criteria are met at the same postbaseline visit date. The denominator is the number of participants in the B/F/TAF safety analysis set with nonmissing postbaseline value of the tests in evaluation at the same postbaseline visit date.

Participants with AST or ALT $> 3 \times$ ULN, total bilirubin $> 1 \times$ ULN, or ALP $> 1.5 \times$ ULN while on-treatment will also be listed.

In addition, baseline, postbaseline, and change from baseline in AST, ALT, ALP, and total bilirubin will be summarized by treatment group (B/F/TAF and Delayed Switch to B/F/TAF) and visit using descriptive statistics.

In addition, ALT elevation (ie, $ALT > 2 \times \text{Baseline}$ and $ALT > 10 \times \text{ULN}$) and ALT flare, defined as ALT elevations confirmed at two consecutive visits, will be evaluated and listed for participants with HIV/HBV coinfection at baseline. The first occurrence of two or more consecutive ALT elevations will be identified as the ALT flare.

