4. PARTICIPANT POPULATION

4.1. Number of Participants and Participant Selection

Approximately 480 participants who meet the eligibility criteria will be enrolled. Eligible participants with chronic hepatitis C virus (HCV) infection are permitted to enroll. In addition, eligible participants with chronic hepatitis B virus (HBV) infection are permitted to enroll if their baseline regimen contains either TAF or TDF.

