$$\frac{(140 - \text{age in years}) \times (\text{wt in kg}) \times 0.85}{72 \times (\text{serum creatinine in mg/dL})} = \text{CLcr (mL/min)}$$
$$\frac{(140 - \text{age in years}) \times (\text{wt in kg}) \times 0.85}{72 \times (\text{serum creatinine in umol/L}) \times 0.6786} = \text{CLcr (mL/sec)}$$
- 11) Normal ECG (or if abnormal, determined by the investigator not to be clinically significant)
- 12) Hepatic transaminases (AST and ALT) \leq 5 \times upper limit of normal (ULN)
- 13) Total bilirubin \leq 1.5 mg/dL (\leq 26 umol/L), **or** normal direct bilirubin
- 14) Adequate hematologic function (absolute neutrophil count \geq 750/mm³ (\geq 0.75 GI/L); platelets \geq 50,000/mm³ (\geq 50 GI/L); hemoglobin \geq 8.5 g/dL (\geq 85 g/L))
- 15) Serum amylase \leq 5 \times ULN (participants with serum amylase > 5 \times ULN will remain eligible if serum lipase is \leq 5 \times ULN)
- 16) Persons of childbearing potential (as defined in [Appendix 6](#)) must have a negative serum pregnancy test at screening and clinic admission.
- 17) Male participants and persons of childbearing potential who engage in heterosexual intercourse must agree to use protocol specified method(s) of contraception as described in [Appendix 6](#)
- 18) Participants must agree to refrain from egg donation from first dose of FDC of B/F/TAF and throughout the study period as described in [Appendix 6](#).
- 19) Life expectancy \geq 1 year

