2.2. Final Analysis

The final statistical analysis will be conducted after all participants either complete the study or prematurely discontinue from the study.

This SAP describes the analysis plan for the final analysis. This final analysis will include all data from the participants randomized to FDC of B/F/TAF and post Week 24 (delayed switch) data for participants randomized to SBR. Data for the first 24 weeks for the SBR group were presented in the Week 24 and Week 48 analyses and will not be summarized in the final analysis. However, all data (other than patient-reported outcomes) will be included in the listings.

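### The liver-threshold rows in SAP 7.2.4 ignore baseline, and no planned summary splits the > 3 x ULN, bilirubin > 2 x ULN, ALP or combined rows by baseline status

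*SAP*

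**What the plan says.** SAP 7.2.4 introduces its threshold tables with "Liver-related abnormalities after initial study drug dosing will be examined and summarized for the B/F/TAF, Delayed Switch to B/F/TAF, and All B/F/TAF groups". They report "the number and percentage of participants who were reported to have the following laboratory test values for post baseline measurements". The rows are AST, ALT, and AST or ALT above 3, 5, 10 and 20 x ULN; total bilirubin above 1 and 2 x ULN; ALP above 1.5 x ULN; and three combined rows. Those pair AST or ALT > 3 x ULN with total bilirubin > 1.5 x ULN, with bilirubin > 2 x ULN, and with bilirubin > 2 x ULN plus ALP < 2 x ULN.

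The counting rule is "For individual laboratory tests, participants will be counted once based on the most severe postbaseline value". For the combined rows, "participants will be counted once when the criteria are met at the same postbaseline visit date". The denominator requires a post-baseline value and does not remove anyone already above the cut-off.

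On entry, Protocol 4.2 criterion 12 admits AST and ALT up to 5 x ULN. Criterion 13 is satisfied by total bilirubin of at most 1.5 mg/dL or, alternatively, by a normal direct bilirubin. Neither Protocol 4.2 nor 4.3 lists an ALP limit. Protocol 4.1 adds: "Eligible participants with chronic hepatitis C virus (HCV) infection are permitted to enroll". It also admits chronic HBV if the baseline regimen contains TAF or TDF.

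On the comparator, SAP 2.2 says of the final analysis: "Data for the first 24 weeks for the SBR group were presented in the Week 24 and Week 48 analyses and will not be summarized".

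**The concern.** A post-baseline count answers whether a participant was ever above the cut-off after dosing. It does not answer whether the elevation arose after dosing. Where entry admits values already above the cut-off, the two questions can have different answers, and the table does not show by how much. The final analysis has no concurrent arm against which to judge the background.

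The combined rows matter most. They are the rows a safety reader turns to first, and one or two pre-existing cases would change how such a row is read. They also have no baseline-adjusted counterpart among the planned summaries.

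**Working it through.** The plan states no expected count for these rows, so there is no figure to reproduce. The check applies the SAP's two rules to the same example values.

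**Inputs**
- Row rule: SAP 7.2.4, post-baseline value above the cut-off.
- Treatment-emergent rule: SAP 7.2.2.1, a rise of at least one grade from baseline.
- Grades: Protocol Appendix 4. AST/ALT Grade 2 is > 2.5 to 5, Grade 3 is > 5 to 10 and Grade 4 is > 10 x ULN. Bilirubin Grade 1 is > 1.0 to 1.5 and Grade 2 is > 1.5 to 2.5 x ULN. ALP Grade 1 is 1.25 to 2.5 x ULN.
- Baseline: SAP 3.8.1, the last value on or before the first B/F/TAF dose. For the Delayed Switch group this falls at about Week 24.

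**Step 1. Two rules, same data (values in x ULN)**

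| Test | Baseline to post | 7.2.4 cut-offs exceeded | Grade change | Treatment-emergent? |
|---|---|---|---|---|
| ALT | 4 to 4 | > 3 | 2 to 2 | No |
| ALT | 4 to 3.1 (a fall) | > 3 | 2 to 2 | No |
| ALT | 5 to 5 | > 3 | 2 to 2 | No |
| ALT | 1 to 4 | > 3 | 0 to 2 | Yes |
| ALT | 4 to 6 | > 3, > 5 | 2 to 3 | Yes |
| Bilirubin | 1.3 to 1.3 | > 1 | 1 to 1 | No |
| Bilirubin | 2.2 to 2.2 | > 1, > 2 | 2 to 2 | No |
| Bilirubin | 1 to 2.2 | > 1, > 2 | 0 to 2 | Yes |

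**Step 2. Rows that an unchanged, eligible screening value can reach**
- AST/ALT: at most 5 x ULN, so only the > 3 row, not > 5, > 10 or > 20.
- Bilirubin, first branch of criterion 13: with ULN assumed at 1.0 to 1.3 mg/dL, 1.5/1.3 = 1.15 and 1.5/1.0 = 1.5 x ULN. This reaches the > 1 row but not > 1.5.
- Bilirubin, second branch: no cap on the total, so > 2 is reachable.
- ALP: no entry limit, so > 1.5 is reachable.
- Combined rows: stable ALT of 4 x ULN, bilirubin of 2.2 x ULN with normal direct bilirubin, and ALP below 2 x ULN meets all three.
- Delayed Switch: baseline is reset at the first B/F/TAF dose and no liver-test limit is stated for the switch. A value that arose during the first 24 weeks has no stated cap and could reach any row.

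**Step 3. Rows that already have a baseline-adjusted count**
- AST/ALT > 5 x ULN: yes, treatment-emergent Grade 3 or 4.
- AST/ALT > 10 x ULN: yes, treatment-emergent Grade 4.
- Bilirubin > 1 x ULN: yes, treatment-emergent Grade 1 or higher.
- AST/ALT > 3 and > 20, bilirubin > 2, ALP > 1.5 x ULN: no grade boundary coincides with the cut-off.
- Combined rows: none. Grades are per test.

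The ALT elevation and flare definitions in 7.2.4 do use baseline, but only for participants with HBV coinfection at baseline and only above 10 x ULN.

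**Step 4. Size, by assumption**

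Affected = N x share entering above 3 x ULN x share still above after dosing.
- Low: 480 x 0.005 x 0.5 = 1.2 (0.25%).
- High: 480 x 0.02 x 1.0 = 9.6 (2.0%).

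**The case against.** The best defence is that the tables do what they say. They are described as post-baseline measurements. The SAP reserves the treatment-emergent label for the grade-rise rule in 7.2.2.1 and never calls the 7.2.4 rows new or drug-related. An all-values screen is a legitimate choice because it cannot miss a case. All of that stands, and it is why the all-values count should stay.

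Other outputs also help:
- SAP 7.2.4 plans change from baseline by visit for AST, ALT, ALP and total bilirubin. It also lists participants above the lowest single-test cut-offs while on treatment.
- SAP 7.2 lists chemistry results by participant in date order, and SAP 2.2 keeps pre-switch data in the listings.
- SAP 8.1 gives separate liver summaries for baseline HBV coinfection, and SAP 8.2 gives listings for HCV.
- Protocol 4.3 excludes decompensated cirrhosis and recent acute hepatitis.

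These outputs let a reader trace a case by hand. None gives a baseline-split count for the rows left open in Step 3.

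Three stronger readings are tempting, and the documents do not support them.
- A reader might infer that every liver row is inflated. Step 2 shows that an unchanged eligible AST/ALT cannot reach > 5 x ULN or above, and Step 3 shows that some rows already have an adjusted count.
- A reader might infer that reported rates would be about twice the true new rate. That follows only if the assumed background rate is set equal to the assumed new rate, and the documents give neither.
- A reader might infer that the SBR background was never shown. SAP 2.2 says it was presented in the Week 24 and Week 48 analyses. The plans for those analyses are not among the documents, so this cannot be checked.

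**Conclusion.** The point holds in a limited form. SAP 7.2.4 applies no baseline condition in numerator or denominator, and entry allows values above several of its cut-offs. Persistent or improving pre-existing elevations can therefore appear as post-dose abnormalities in the AST/ALT > 3 x ULN, bilirubin, ALP and combined rows, and in the Delayed Switch group in any row. What is missing is a baseline-split count, chiefly for AST/ALT > 3 x ULN, bilirubin > 2 x ULN, ALP > 1.5 x ULN and the combined criteria.

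The 1 to 10 participants are an illustration resting on assumed entry and persistence rates, and they concern AST/ALT > 3 x ULN only. No count can be put on the combined rows; pre-existing cases there need two permitted elevations in the same person. This is a minor improvement to a descriptive safety table, with no bearing on efficacy, alpha or power.

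**What to change.** In SAP 7.2.4, keep each row's all-values count and add two sub-rows: participants who did not meet that row's criterion at baseline, and participants who already did. Use the SAP 3.8.1 baseline, the last value on or before the first B/F/TAF dose. For combined rows, apply the whole criterion to the baseline values, so that someone with raised ALT at baseline and newly raised bilirubin counts as new. Keep one denominator so that the sub-rows add up to the all-values count. Where baseline is missing, follow 7.2.2.1 and count the participant as new.

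This matches the SAP's own practice. Treatment-emergent grades use baseline (7.2.2.1), proteinuria is shown by baseline grade (7.2.5.2), and new use of lipid-modifying drugs excludes baseline users (Appendix 6, item 15).

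The cost is one baseline flag per row and a few extra table lines, from data already collected. SAP Section 1 provides for recording changes made after finalization in the clinical study report.

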7.2.5. Renal-Related Laboratory Evaluations

7.2.5.1. Serum Creatinine and eGFR_{CG}

Baseline, postbaseline, and change from baseline in serum creatinine and eGFR_{CG} will be summarized by treatment group (B/F/TAF and Delayed Switch to B/F/TAF) and visit using descriptive statistics.

Median (Q1, Q3) of change from baseline in serum creatinine and eGFR_{CG} over time will be plotted by treatment group.

Summary of baseline, postbaseline, and change from baseline in serum creatinine and eGFR_{CG} will be repeated within each subgroup of baseline ARV medication (see Section 3.4.2).

7.2.5.2. Proteinuria by Urinalysis (Dipstick)

The proteinuria by urinalysis (dipstick) toxicity grade (Grade 0 to Grade 3) will be summarized by baseline proteinuria toxicity grade and treatment group (B/F/TAF and Delayed Switch to B/F/TAF) by visit. In addition, the last on-treatment proteinuria toxicity grade will be summarized by baseline proteinuria toxicity grade and treatment group. On-treatment data is as all data collected up to 1 day after permanent discontinuation of study drug.

7.3. Body Weight, Height, and Vital Signs

Descriptive statistics will be provided by treatment group (B/F/TAF and Delayed Switch to B/F/TAF) for vital signs and body weight as follows:

- Baseline values
- Values at each postbaseline analysis window
- Change from baseline to each postbaseline analysis window

A baseline value will be defined as the last nonmissing value obtained on or prior to the date of first dose of study drug. Change from baseline to a postbaseline visit will be defined as the postbaseline value minus the baseline value.

In the case of multiple values in an analysis window, data will be selected for analysis as described in Section 3.8.3. No formal statistical testing is planned.

A by-subject listing of vital signs will be provided by subject ID number and visit in chronological order. In the same listing, a by-subject listing of body weight, height, and BMI will be provided.

7.4. Prior and Concomitant Medications

7.4.1. Nonstudy Drug Antiretroviral Medications

Any nonstudy drug antiretroviral (ARV) medications used prior to, during, or after the study (if collected) will be coded using the Gilead-modified WHO Drug Dictionary for ARV medications. The WHO preferred drug name and drug code will be attached to the clinical database. All nonstudy drug ARV medications will be listed.

7.4.2. Concomitant Non-ARV Medications

Concomitant non-ARV medications (ie, medications other than study drug that are taken while receiving study drug) will be coded using the WHO Drug Dictionary. The WHO Drug preferred drug name and drug code will be attached to the clinical database. Use of concomitant medications from the date of first dose of study treatment up to the date of last dose of study treatment will be summarized (number and percentage of participants) by treatment group (B/F/TAF and Delayed Switch to B/F/TAF) and preferred drug name. Multiple drug use will be counted only once per participant for each preferred drug name. The summary will be sorted by decreasing total frequency. For drugs with the same frequency, sorting will be done alphabetically.

If the start or stop date of non-ARV medications is incomplete, the month and year (or year alone if month is not recorded) of the start or stop date will be used to determine whether the non-ARVs are concomitant or not. The medication is concomitant if the month and year of the start or stop (or year of the start or stop, if month is not recorded) of the medication does not meet either of the following criteria:

- The month and year of start of the medication is after the date of the last dose of study drug
- The month and year of stop of the medication is before the date of the first dose of study drug

If the start and stop date of non-ARV medications are complete, the start date is not after last dose date and the stop date is not before first dose date, or the non-ARV medications are marked as ongoing and start date is on or before last dose date, the non-ARV medications are concomitant.

Summaries of non-ARV concomitant medications will be provided for the B/F/TAF safety analysis set. Participants with any non-ARV concomitant medications will be listed. No inferential statistics will be provided.

7.5. Electrocardiogram Results

A by-subject listing for electrocardiogram (ECG) assessment results will be provided.

7.6. Other Safety Measures

A data listing will be provided for participants experiencing pregnancy during the study. Physical examination data was not collected in the eCRF. Therefore, it will not be included in the analysis.

7.7. Subject Subgroup for Safety Endpoints

Incidence of all treatment-emergent AEs will be repeated within each subgroup defined in Section 3.4.2 using the B/F/TAF safety analysis set.

7.8. Changes from Protocol-Specified Safety Analyses

No changes from the protocol-specified safety analyses are planned.

8. SPECIAL POPULATION ANALYSES

8.1. Analyses for HIV/HBV Coinfected Participants

Participants with HIV/HBV coinfection at baseline are defined as participants who meet any of the following two criteria:

- Positive HBsAg on or prior to the first dose date, or
- Negative HBsAg, negative HBsAb, positive HBcAb, and quantifiable HBV DNA (ie, HBV DNA \geq 20 IU/mL) on or prior to the first dose date.

The following analyses will be conducted by treatment (B/F/TAF, and Delayed Switch to B/F/TAF) for participants with HIV/HBV coinfection at baseline:

- Treatment-emergent adverse events overall summary
- Treatment-emergent adverse events by SOC, HLT, and PT
- Treatment-emergent laboratory abnormalities
- The change from baseline for liver-related laboratory tests, including ALT, AST, ALP, total bilirubin, direct and indirect bilirubin.

Listings will be provided for:

- adverse events
- liver-related laboratory tests and HBV DNA results
- ALT elevation (ie, ALT $>$ 2 x Baseline and ALT $>$ 10 x ULN) and ALT flare (see section [7.2.4](#))

Participants with incident HIV/HBV coinfection while on study drug are defined as participants who are not HIV/HBV coinfecting at baseline and meet any of the following criteria:

- Positive HBsAg after the first B/F/TAF dose date and on or prior to the last B/F/TAF dose date, or
- Negative HBsAg, negative HBsAb, positive HBcAb, and quantifiable HBV DNA (ie, HBV DNA \geq 20 IU/mL) after the first B/F/TAF dose date and on or prior to the last B/F/TAF dose date, or

- Experience any of the following adverse events (ie, selected MedDRA PTs from the SMQ of “Liver Infections”) with onset date after the first B/F/TAF dose date and on or prior to the last B/F/TAF dose date: Acute hepatitis B, Chronic hepatitis B, Congenital hepatitis B infection, Hepatitis B, Hepatitis B core antibody positive, Hepatitis B DNA assay positive, Hepatitis B surface antigen positive, Hepatitis B virus test positive.

The following listings will be provided for participants with incident HIV/HBV coinfection while on study drug:

- Listing of adverse events
- Listing of liver-related laboratory tests and HBV DNA results

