8.5.1.1. US FDA-defined Snapshot Algorithm

All HIV-1 RNA data collected on-treatment (ie, including data collected up to 1 day after the last dose date of study drug) will be used in the snapshot algorithm. Virologic outcome will be defined as the following categories:

- **HIV-1 RNA < 50 copies/mL:** this includes participants who have the last available on-treatment HIV-1 RNA < 50 copies/mL in the Week 24 analysis window
- **HIV-1 RNA ≥ 50 copies/mL:** this includes participants
 - a) Who have the last available on-treatment HIV-1 RNA ≥ 50 copies/mL in the Week 24 analysis window, or
 - b) Who do not have on-treatment HIV-1 RNA data in the Week 24 analysis window and
 1. Who discontinue study treatment prior to or in the Week 24 analysis window due to lack of efficacy, or
 2. Who discontinue study treatment prior to or in the Week 24 analysis window due to reason other than lack of efficacy and have the last available on-treatment HIV-1 RNA ≥ 50 copies/mL
- **No Virologic Data in the Week 24 Analysis Window:** this includes participants who do not have on-treatment HIV-1 RNA data in the Week 24 analysis window because of the following:
 - a) Discontinuation of study treatment prior to or in the Week 24 analysis window due to reasons other than lack of efficacy and the last available on-treatment HIV-1 RNA < 50 copies/mL, or
 - b) Missing data during the window but on study treatment

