7.2. Laboratory Evaluations

Laboratory data collected during the study will be analyzed and summarized using both quantitative and qualitative methods. Summaries of laboratory data will be provided for the B/F/TAF safety analysis set and will include data collected up to the last dose of B/F/TAF study drug plus 30 days.

The analysis will be based on values reported in conventional units. When values are below the LOQ, they will be listed as such, and the imputed value will be used for the purpose of calculating summary statistics as specified in Section 3.7.

A by-subject listing for laboratory test results will be provided by subject ID number and visit in chronological order for hematology, serum chemistry, and urinalysis separately. Values falling outside of the reference range and/or having a severity grade of 1 or higher on the Gilead Grading Scale for Severity of Adverse Events and Laboratory Abnormalities will be flagged in the data listings, as appropriate.

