8.2. Analyses for HIV/HCV Coinfected Participants

Participants with HIV/HCV coinfection at baseline are defined as participants with positive HCVAb and quantifiable HCV RNA (ie, HCV RNA \geq 15 IU/mL) on or prior to the first dose date. The following listings will be provided for participants with HIV/HCV coinfection at baseline:

- Listing of adverse events
- Listing of liver-related laboratory tests and HCV RNA results

Participants with incident HIV/HCV coinfection while on study drug are defined as participants who are not HIV/HCV coinfecting at baseline and meet any of the following criteria:

- Positive HCVAb after the first B/F/TAF dose date and on or prior to the last B/F/TAF dose date, or
- Quantifiable HCV RNA (ie, HCV RNA \geq 15 IU/mL) after the first B/F/TAF dose date and on or prior to the last B/F/TAF dose date, or
- Experience any of the following adverse events (ie, selected MedDRA PTs from the SMQ of “Liver Infections”) with onset date after the first B/F/TAF dose date and on or prior to the last B/F/TAF dose date: Acute hepatitis C, Chronic hepatitis C, Hepatitis C, Hepatitis C antibody positive, Hepatitis C RNA positive, Hepatitis C virus test positive.

The following listings will be provided for participants with incident HIV/HCV coinfection while on study drug:

- Listing of adverse events
- Listing of liver-related laboratory tests and HCV RNA results

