- n Chemistry profile: alkaline phosphatase, AST, ALT, total bilirubin, direct and indirect bilirubin, total protein, albumin, CPK, bicarbonate, BUN, calcium, chloride, creatinine, glucose, phosphorus, magnesium, potassium, sodium, amylase, and Cystatin C. After Day 1, calcium, phosphorous, magnesium, and amylase (reflex lipase testing is performed in participants with total amylase $> 1.5 \times$ ULN) will not be collected. Analyses of glucose will be done as part of the fasting metabolic assessments, and not as part of the chemistry profile at Day 1, Weeks 24, 48, and 72. Cystatin C will only be collected at Day 1.
- o Metabolic Assessments will be performed at Day 1, Weeks 24, 48, and 72. Fasting (no food or drinks, except water, at least 8 hours prior to blood collection) glucose and lipid panel (total cholesterol, HDL, direct LDL, triglycerides). If the participant has not fasted prior to the visit, the visit may proceed, but the participant must return within 72 hours in a fasted state to draw blood for the metabolic assessments.
- p CBC with differential and platelet count.
- q HIV 1 genotype and phenotype testing for participants with confirmed virologic failure and HIV 1 RNA >200 copies/mL. Following virologic rebound, participants will be asked to return to the clinic (2-3 weeks later) prior to the next scheduled visit or at the next scheduled study visit for a HIV 1 RNA and HIV 1 resistance analysis (reverse transcriptase, protease, and integrase genotype and phenotype) blood draw. Based on the results of this testing, participants should be managed according to the Virologic Rebound Schema.
- r [REDACTED]
- s HBV blood panel will be performed at Screening and Week 48: HBsAg, HBsAb, HBcAb.
- t **For participants who are HBV co-infected (defined in Protocol Section 6.9.1):** The following HBV Blood panel will be conducted by the central laboratory: HBsAb, HBsAg (qualitative and quantitative), and HBeAg (if negative, reflex HBeAb).
For participants who are NOT HBV co-infected: The following HBV Blood panel will be conducted by the central laboratory: HBsAb, HBcAb, and HBsAg. Participants who are HBsAg or HBcAb positive will have a reflex test for HBV DNA (viral load).
- u **For participants who are HBV co-infected:** Plasma HBV DNA will be collected at Day 1, Week 24, Week 48 and ESDD.
- v Hepatitis C virus serology will be performed at Screening, Week 48, and Week 72. Participants who are HCVAb positive will have an HCV RNA test performed.

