Appendix 2. Flowchart of US FDA-defined Snapshot Algorithm (for Switch Trial)

The following flowchart for US FDA-defined snapshot algorithm is based on the US FDA Guidance on Human Immunodeficiency Virus-1 Infection: Developing Antiretroviral Drugs for treatment {[U. S. Department of Health and Human Services 2015](#)}.

* On-Treatment HIV-1 RNA data include all HIV-1 RNA data for subjects who are on-going and HIV-1 RNA data up to 1 day after the last dose date of study drug for subjects who prematurely discontinue or complete study drug.

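### Incident HBV/HCV coinfection closes at the last B/F/TAF dose date and opens from Screening serology, so a Week 48 positive can be left out or, in Delayed Switch, mislabelled as on study drug

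*SAP*

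**What the plan says.** SAP 8.1 gives three routes to incident HBV coinfection while on study drug, for participants not coinfected at baseline. The first is "Positive HBsAg after the first B/F/TAF dose date and on or prior to the last B/F/TAF dose date". The second, a serology pattern with quantifiable HBV DNA, has the same two date limits. The third, a list of adverse event terms, applies "with onset date after the first B/F/TAF dose date and on or prior to the last B/F/TAF dose date". SAP 8.2 does the same for HCV, starting with "Positive HCVAb after the first B/F/TAF dose date and on or prior to the last B/F/TAF dose date", then quantifiable HCV RNA, then adverse event terms. SAP Appendix 6, item 18, adds that the tests must share an accession number. It adds no days to the date limit.

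On the schedule, SAP Appendix 1 states "HBV blood panel will be performed at Screening and Week 48: HBsAg, HBsAb, HBcAb". HCV serology is at Screening, Week 48 and Week 72. Neither is scheduled at Week 24, at the early discontinuation visit or at the 30-Day Follow-Up Visit.

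Other windows in the documents are wider:

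- Laboratory summaries (SAP 7.2): "will include data collected up to the last dose of B/F/TAF study drug plus 30 days".
- Treatment-emergent adverse events (SAP 7.1.5.1): onset up to 30 days after permanent discontinuation.
- Last on-treatment proteinuria grade (SAP 7.2.5.2): "On-treatment data is as all data collected up to 1 day after permanent discontinuation of study drug".
- Snapshot HIV-1 RNA: "HIV-1 RNA data up to 1 day after the last dose date of study drug" (SAP Appendix 2), and likewise "including data collected up to 1 day after the last dose date of study drug" (Protocol 8.5.1.1).

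SAP 3 states that permanent discontinuation includes completing study drug, so these windows also cover participants who finish as planned.

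**The concern.** The definition depends on one or two scheduled tests, and both of its date limits fit that schedule poorly.

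At the upper end, a participant who leaves at Week 48 has the only scheduled post-baseline serology for both viruses at the final visit. No section of the protocol or SAP requires a dose on that day before the draw. Someone who doses in the evening and returns the bottle at the visit may have a last dose on the day before. A new positive would then fall outside every route.

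At the lower end, the first B/F/TAF dose in Delayed Switch comes at about study Week 24, but no serology is scheduled then. A positive at study Week 48 may reflect infection on the old regimen, yet it carries the on-study-drug label.

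At stake is whether the listings show the people they are meant to show. Newly detected HBV in someone stopping B/F/TAF is a case that a safety reader would look for, since Protocol 7.6.4.2 deals with hepatitis B exacerbation after stopping.

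**Working it through.** The plan gives no figure to reproduce. The check compares date rules with the schedule.

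**Upper limit, immediate-switch group.** Place the Week 48 draw on its nominal day, 48 × 7 = Day 336. A positive counts if 336 ≤ last dose day + k, where k is the number of days allowed after the last dose.

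| Last dose | SAP 8.1/8.2 (k = 0) | k = 1 | k = 30 |
|---|---|---|---|
| Day 336 | ≤ 336: counted | ≤ 337: counted | ≤ 366: counted |
| Day 335 | ≤ 335: left out | ≤ 336: counted | ≤ 365: counted |
| Day 334 | ≤ 334: left out | ≤ 335: left out | ≤ 364: counted |

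A participant leaving at Week 48 has one scheduled post-baseline test per virus. With a last dose on Day 335, 0 of 1 can count under the present rule. Allowing 1 day rescues only that case; 30 days also covers longer gaps.

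**How the last dose date is set.** SAP 3.8.1 takes the latest recorded B/F/TAF end date, which is not tied to the visit. Under SAP Appendix 6, item 22, a partial date (month and year known) is imputed from the 15th, bottle dispensing dates, and study drug start and end dates, without visit dates. It can therefore fall before a draw later in the month. A missing date (completely missing, or only the year known) is imputed using clinic and laboratory dates, and the sample would then count.

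**Adverse event route.** It has the same upper limit, so an event with onset on the draw date does not rescue the case.

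**Lower limit, Delayed Switch.** SAP 3.8.1 defines Study Day 1 as the first B/F/TAF dose. SAP Appendix 6, item 18, takes the latest result on or before that date as baseline. HBV DNA at Week 24 is only for participants already coinfected, so the scheduled baseline serology is the Screening sample, up to 30 days before the Day 1 visit (Protocol 6.2.1).

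- Screening close to Day 1: 24 of 48 weeks between serologies precede B/F/TAF, 24/48 = 50%.
- Screening 30 days before: 30/7 = 4.3 weeks; (24 + 4.3)/(48 + 4.3) = 28.3/52.3 = 54%.

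So half or slightly more of the interval in which the infection could have been acquired lies before the first B/F/TAF dose.

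**Number affected.** At the upper limit this is the number of new positives at the final draw among participants whose last recorded dose came earlier. The documents give no share leaving at Week 48, no dosing pattern on visit days and no rate of new infection. It cannot be computed.

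**The case against.** The strongest reply is that this is an explicit, reproducible rule feeding a small output. SAP 8.1 and 8.2 plan two by-participant listings per virus for incident cases, with no rate, denominator or comparison. Status is only yes or null, so a negative test outside the window changes nothing. That stands and keeps the point minor. SAP 7.1.6 and 7.7, read literally, would repeat adverse event summaries in every subgroup of SAP 3.4.2, including incident coinfection, but those too are descriptive.

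It can also be said that 1 day is not a general rule of the SAP. It is stated for the snapshot and for proteinuria, while concomitant medication (SAP 7.4.2) and new lipid-modifying medication (SAP Appendix 6, item 15) close at the last dose date, as here. That is correct. Those items, however, concern drug use recorded by date and do not hang on a single scheduled test at the final visit. For laboratory data and adverse events in general, the SAP's window is 30 days.

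Finally, the Delayed Switch problem comes from the visit schedule, and moving the upper limit does not touch it. That also stands, which is why it needs its own label.

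Some stronger readings are tempting but unsupported:

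- **Results are thrown away.** They are not. SAP 2.2 and 7 keep them in the data listings, and a hepatitis adverse event within 30 days still enters the treatment-emergent summaries. Only the incident classification is lost.
- **A sizeable share of participants has an unusable test.** Such a figure would need assumed leaving and dosing patterns, and would count tests when only new positives matter.
- **160 Delayed Switch participants are affected.** 160 is the planned SBR randomization. Delayed Switch (SAP 3.2) includes only those who switched and took at least one dose, and only newly infected participants could be mislabelled.
- **The SAP blames B/F/TAF for these infections.** The listing makes no causal or comparative claim. The fault is a label about timing that the data cannot support.

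**Conclusion.** The point holds as a classification fault at both ends of the window. Followed exactly, SAP 8.1 and 8.2 can omit a new positive found at the final scheduled test, and can label as on study drug an infection acquired on the old regimen. The first needs a last recorded dose before the draw in a participant leaving at Week 48; participants who continue past Week 48 are not exposed to it at that draw. The second needs a Delayed Switch participant infected before the first B/F/TAF dose and first detected at study Week 48, and assumes no unscheduled serology in between.

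The impact is minor. It is confined to descriptive safety output and leaves the primary and secondary efficacy endpoints untouched. No count of affected participants can be derived from the documents.

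**What to change.** In SAP 8.1 and 8.2, move the upper limit for the laboratory and adverse event routes alike to the last B/F/TAF dose date plus 30 days, matching SAP 7.2 and 7.1.5.1. Changing the laboratory routes alone would leave two cut-offs in one definition.

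Label Delayed Switch cases first detected at study Week 48 as 'acquired between Screening and Week 48'.

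The cost is one date condition in the program, one label and a few words in the SAP. The downside is that some cases detected shortly after the last dose would be included, so the heading should read 'detected up to 30 days after last dose'. Anyone who stopped B/F/TAF more than 30 days before the Week 48 draw would still be left out, in keeping with the purpose of the definition.
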